15.3.9.2. ANALYSIS

The analysis for BILAG SLE flares (moderate, severe, moderate or severe) will replicate that performed for SRI. Flare-free survival will be analyzed as detailed for SELENA flares (Section 15.3.8.2). The number of domains exhibiting a new A or B scores will be tabulated.

15.3.10. RENAL FLARES

Renal flares are defined as in Section 6.2.2 of the study protocol, and occurrences are captured on the eCRF.

15.3.10.1. DERIVATION

The time to first flare will be calculated in days as defined in Section 15.1.

15.3.10.2. ANALYSIS

The analysis for occurrence of renal flares will replicate that performed for SRI. Flare-free survival will be estimated as detailed for SELENA flares (Section 15.3.8.2).

15.3.11. ACTIVE RENAL DISEASE

Active Renal disease is defined as in Section 6.2.2 of the study protocol, and occurrences are captured on the eCRF.

15.3.11.1. DERIVATION

The time to first diagnosis will be calculated in days as defined in Section 15.1.

15.3.11.2. ANALYSIS

The analysis for occurrence of active renal disease will replicate that performed for SRI. Flare-free survival endpoints will be analyzed as detailed for SELENA flares (Section 15.3.8.2).

15.3.12. CONCOMITANT USE OF ORAL CORTICOSTEROIDS

Use of oral corticosteroids is collected continuously in the concomitant medication panel of the eCRF and will be identified using the WHO anatomical therapeutic class.

15.3.12.1. DERIVATION

Corticosteroid usage will be assessed (present vs absent) for each postdose visit, as the interval starting with the date following the previous visit and ending with the date of the current visit (inclusive).

The time to first usage of oral corticosteroids will be calculated in days as defined in Section 15.1.

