## 2.0 INTRODUCTION

### 2.1 Background

Systemic lupus erythematosus (SLE) is a chronic, multisystem, disabling autoimmune condition, which predominantly affects women of childbearing years. Its prevalence in the United States (US) is estimated to be approximately 52.2/100,000, with the highest incidence between 15 to 44 years of age at a female-to-male ratio as high as 12:1. Clinical manifestations can involve multiple organ systems, including rash and alopecia, renal disease, inflammatory arthritis, serositis, vasculitis, autoimmune cytopenias, cognitive dysfunction and other central nervous system (CNS) involvement, and constitutional symptoms, all leading to significant morbidity including reduced physical function, employment loss, lower health-related quality of life, and reduced lifespan.

Treatment options for SLE remain relatively limited. Some, particularly milder, cases of SLE may respond to treatment with oral antimarial agents such as hydroxychloroquine, but moderate-to-severe disease, particularly involving critical systems such as renal or CNS, often involves immunosuppressive therapies, including oral immunosuppressants such as mycophenolate mofetil or azathioprine, as well as cyclophosphamide, calcineurin inhibitors, and B cell depleting therapy with rituximab. The anti-B lymphocyte stimulator therapy, belimumab, may be particularly helpful in patients with mucocutaneous and/or musculoskeletal manifestations, but the treatment effect remains relatively small. Regardless of the specific therapy chosen, the majority of patients continue to require long-term corticosteroid therapy, resulting in long-term morbidity and mortality. Novel therapeutic options, therefore, are urgently needed.

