### **5.7.2      Allowed Medications**

If taking the following medications, the subject must be on a stable dose prior to the baseline visit for at least the durations indicated and be willing and able to continue at stable doses throughout the study:

- corticosteroids (up to 40 mg/day prednisone or equivalent): 4 weeks;
- hydroxychloroquine or other antimalarials: 3 months;
- mycophenolate mofetil, mycophenolic acid, azathioprine, methotrexate, leflunomide, or 6-mercaptopurine: 3 months;
- NSAIDS and COX-2 inhibitors at or below the maximum approved dose: 2 weeks; or
- Oral, injected, or implanted hormonal methods of contraception, as well as HRT: 3 months.

Temporary increases in corticosteroid dosage (“bursts”) are permissible during the study as follows.

- The maximum duration of a burst is limited to 14 days duration on no more than 2 occasions.
- The corticosteroid dose must return to the preburst dose or lower at least 1 week before the 12-week assessments.
- The maximum dosage during a burst is up to 0.5 mg/kg prednisone, or equivalent, including any other steroids being given.

- The specific dose and taper schedule is at the discretion of the Investigator.

No increases in corticosteroid dosage outside of bursts are permitted. Decreases in the maintenance corticosteroid dose are allowed.

MMAE is primarily metabolized by cytochrome P450 enzyme 3A4 (CYP3A4), and is a substrate of P-glycoprotein (P-gp). Caution should be used in co-administering drugs which strongly inhibit CYP3A4 or P-gp, since increased MMAE exposures may result.

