15.1. GENERAL METHODOLOGY

If subjects are missing assessments during participation in the trial (prior to completion or withdrawal), these will be assumed to be non-events. The denominator used for percentages or proportions in tabulations will be the number of subjects in the analysis set with available data for the corresponding time point and treatment group.

The time to a pre-defined event will be calculated in days for each subject and response/flare as the date of the first event minus the date of randomization. If the date of the event is not recorded, the date of the study visit will be used. When there are multiple criteria to be met, the first event date is defined as the first date on which all criteria are met concurrently. If no flare/event occurred prior to the end of study participation (including for early termination), the time to flare will be regarded as censored at termination.

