15.2.1.2. ANALYSIS

The following analyses will be performed for all study days with Day 85 specified as the secondary endpoint, and all other visits falling under exploratory analyses.

The percentage of subjects demonstrating SRI Response will be presented by treatment with 95% CI using Wilson's score method (SAS PROC FREQ syntax: table response/binomial (wilson)). Comparisons between each active treatment group and placebo will be performed using Fisher's exact test (two-sided). The ratio of percentages (relative risk) for active to placebo will be presented for each dose level with corresponding 95% CI, based on the score method [Farrington] (SAS PROC FREQ syntax: table trta*response / relrisk(method=score equal)). Percentages with Wilson 95% CI will be plotted versus study day per treatment, with all treatments overlain.

Logistic regression of the log odds of SRI response on log2 dose level (mg/kg) will be performed. Placebo subjects will be treated as a having dose of 0 mg/kg. Based on this model, the estimate of the slope and odds ratio (OR) for a doubling of dose will be presented with 95% CI (based on the profile likelihood) and two-sided p-value (Wald test).

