15.3.12.2. ANALYSIS

The analysis for corticosteroid usage will replicate that performed for SRI. Corticosteroid -free survival endpoints will be analyzed as detailed for SELENA flares (Section 15.3.8.2).

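### The oral corticosteroid endpoint has no dose or baseline term, so partial tapers, and bursts on top of maintenance, leave it unchanged

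*SAP*

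**What the plan says.** SAP 15.3.12 takes oral corticosteroid use from the concomitant medication panel. In 15.3.12.1, "Corticosteroid usage will be assessed (present vs absent) for each postdose visit". The window for each visit runs from the day after the previous visit to the current visit. In 15.3.12.2, "The analysis for corticosteroid usage will replicate that performed for SRI". Under SAP 15.2.1.2 that means a two-sided Fisher's exact test of each active dose against placebo, a relative risk, and a logistic regression on dose level.

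SAP 15.3.12.1 adds one further variable: "The time to first usage of oral corticosteroids will be calculated in days as defined in Section 15.1". It does not use dose either.

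Protocol 5.7.2 permits maintenance use: "corticosteroids (up to 40 mg/day prednisone or equivalent): 4 weeks". It also says "Decreases in the maintenance corticosteroid dose are allowed", and it allows up to two bursts of at most 14 days. Protocol 2.1 says of SLE patients generally that "the majority of patients continue to require long-term corticosteroid therapy".

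The arms have 8 subjects per dose and 8 pooled placebo subjects (Protocol 5.3).

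**The concern.** Steroid exposure is a dose, and the SAP cuts it at zero. Take three subjects who all enter on 30 mg/day: one tapers to 5 mg, one stays at 30 mg, one needs a burst. All three are scored present at every visit, although they have done well, the same and badly.

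A steroid-use endpoint would be expected to show steroid sparing and rescue use. In maintenance users this one shows neither, short of complete withdrawal. The study is meant to inform a larger efficacy trial, and a flat steroid table could be taken to mean that the drug has no steroid-sparing effect when the variable could not have shown one.

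Nothing in the SAP's general rules repairs this. Section 7.1 uses the baseline of the dependent variable as a covariate when available, but 15.3.12.1 derives no baseline steroid value. Section 7.5 excludes subgroup analyses, so baseline users will not be shown separately. The continuous efficacy scores, by contrast, are analysed as change from baseline with a baseline covariate (for example CLASI, SAP 15.3.3).

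**Working it through.** The documents give no power, event rate or entry proportion for this endpoint, so there is no figure of the plan's own to reproduce. The only design arithmetic is the arm size: 10 × 4/5 = 8 active and 10 × 1/5 = 2 placebo per cohort, and 4 × 2 = 8 pooled placebo. Everything below is illustration under stated assumptions.

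**Step 1. How much of a burst difference survives the coding.** Let p be the share on steroids at entry and b the share with a burst in the interval, with no complete stops. Then

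P(present) = p + (1 − p)b,

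and the between-arm difference is (1 − p)(b_placebo − b_active). Assume b = 40% on placebo and 10% on active, a true difference of 30 points. Fisher power is by full binomial enumeration, two-sided 5%, 8 v 8.

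| p | present, placebo | present, active | difference | Fisher power | share of present who entered on steroids (placebo / active) |
|---|---|---|---|---|---|
| 30% | 58% | 37% | 21 points | 7.1% | 52% / 81% |
| 50% | 70% | 55% | 15 points | 4.0% | 71% / 91% |
| 70% | 82% | 73% | 9 points | 1.1% | 85% / 96% |
| 90% | 94% | 91% | 3 points | under 0.1% | 96% / 99% |

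For p = 50%: 0.5 + 0.5 × 0.4 = 0.70, 0.5 + 0.5 × 0.1 = 0.55, and 0.5/0.70 = 71%. Letting 10% of the non-burst users stop completely moves the last column by at most about 2 points. A binary variable defined against the subject's own baseline dose keeps the full 30 points at any p, though its power is still only 9.5%.

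**Step 2. Present/absent against change in dose, 8 v 8.** Simulation, assuming 50%, 70% or 90% on steroids at entry, entry doses of 5–30 mg, and 15% of tapers going to zero. Each triple follows that order. Results are approximate and shift by a few points with the burst and taper sizes assumed.

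| Assumed effect (active v placebo) | Fisher, present/absent | Wilcoxon, change in daily dose |
|---|---|---|
| Large: taper 60% v 5%, burst 5% v 40% | 7% / 3% / <1% | 51% / 63% / 72% |
| Moderate: taper 50% v 10%, burst 10% v 30% | 3% / 1% / <1% | 19% / 27% / 33% |
| Small: taper 20% v 10%, burst 10% v 20% | not more than about 2% | 4–7% |

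Another weak scenario (taper 10% v 5%, burst 10% v 30%) gives Wilcoxon about 8%, 10% and 11%.

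**Step 3. Can baseline imbalance create a false signal?** By exact binomial calculation, two arms of 8 differ in entry use by at least 2 subjects (25 points) with probability 45%, 41% and 19% at p = 50%, 70% and 90%. Such gaps are not significant: Fisher p is 0.61 for 4/8 v 6/8 and 0.47 for 6/8 v 8/8. The probability that entry use alone gives p ≤ 0.05 is 2.1%, 1.2% and 0.04%. The test is conservative.

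**Step 4. What the rest of the SAP captures.** Increased or parenteral corticosteroids are a treatment-failure event with Kaplan-Meier analysis (15.3.13). Treatment failure rules out BICLA response (15.3.2). Prednisone increases are SELENA flare criteria (15.3.8). Reduction of dose appears in no planned summary or test; SAP 13 provides listings and counts of medication use only.

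**The case against.** The strongest reply is that rescue use is not lost to the plan. Step 4 bears this out: increases are counted in three other places. What goes unmeasured across the plan is partial dose reduction.

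Second, the variable is not blind to everything. A complete stop registers once a whole interval is steroid-free, and a burst in a subject who entered off steroids registers. The section also contains time to first usage. The first two are real exceptions. The third does not help, because it carries no dose, and its time origin ("the date of the first event minus the date of randomization") is of little use for someone already on steroids at randomization.

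Third, the gain from the remedy depends on effects that nobody has specified. Subjects must be willing to continue at stable doses, decreases are only permitted, no taper is scheduled, and there is no steroid-sparing objective. With small effects the dose analysis is nearly as uninformative as the binary one. This stands, and it limits how much can be claimed.

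Fourth, the endpoint is exploratory (SAP 15.3), is not in the protocol's endpoint lists, and has no multiplicity control (SAP 7.4), in a safety study sized by clinical judgment. No decision rests on it. That also stands.

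A reader might infer that chance imbalance in entry steroid use would be mistaken for a drug effect. Step 3 does not support this: imbalance is common, but it seldom reaches nominal significance. A reader might also quote power for all active subjects pooled (32 v 8). The SRI analysis that this endpoint copies names only each active dose against placebo for Fisher's test, so the figures here are confined to 8 v 8.

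**Conclusion.** The point holds as one of insensitivity. In subjects who enter on permitted maintenance steroids, a partial taper or a burst on top of maintenance cannot change the SAP 15.3.12.1 variable, and dose reduction is not summarised or tested anywhere in the plan. That much follows from the text.

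The size of the loss rests on assumptions. With 50–90% on steroids at entry and 8 per arm, the planned test has about 7% power or less in every scenario tried. The dose-change analysis ranges from about 50–70% under a large effect down to under 10% under the small one. That the variable mostly reflects who entered on steroids is an inference from assumed entry use: it holds at 50–90%, while at 30% the placebo arm is near break-even (52%). Protocol 2.1 describes SLE patients in general and does not fix the share in this trial.

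This is a low-cost improvement to an exploratory endpoint. It does not threaten the trial's safety objective or its SRI analysis.

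**What to change.** First confirm that the eCRF captures steroid dose. Protocol 5.7 requires start and stop dates and the reporting of changes, but does not name dose. The stable-dose entry criterion, the burst limits and the mg/kg flare criteria all imply that dose is known at the site; they do not show that it is in the database in analysable form.

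Then, in SAP 15.3.12.1 and 15.3.12.2, before unblinding:

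- derive each subject's mean daily oral prednisone-equivalent dose at baseline and in each visit interval;
- analyse change from baseline dose by Wilcoxon rank-sum, or by rank ANCOVA with baseline dose as covariate, for each dose and all active against placebo;
- if a binary variable is kept, define it against the subject's own baseline dose: any increase above it, and separately any reduction below it.

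The cost is SAP wording, a prednisone-equivalent conversion table and a convention for partial dose dates. No treatment rule changes. If dose is not in the database, the SAP should say that this endpoint cannot show partial tapers, or bursts in maintenance users.

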15.3.12.2. ANALYSIS

The analysis for corticosteroid usage will replicate that performed for SRI. Corticosteroid -free survival endpoints will be analyzed as detailed for SELENA flares (Section 15.3.8.2).

15.3.13. TREATMENT FAILURE

Treatment failure is defined as meeting at least one of the following criteria, and will be recorded on the eCRF:

- Death
- Premature withdrawal from the study due to adverse events or lack of efficacy
- Addition of new or increased immunosuppressive or antimalarial or increased or parenteral corticosteroids.

15.3.13.1. DERIVATION

The time to treatment failure will be to the first occurrence of the above events, calculated in days as defined in Section 15.1.

15.3.13.2. ANALYSIS

The time to treatment failure will be analyzed as detailed for SELENA flares (Section 15.3.8.2).

15.3.14. HAQ-DI

The Health Assessment Questionnaire (HAQ) Disability Index (DI) assesses patient disability over the past week over 8 daily functions and activities on a scale of 0 to 3, with 0 indicating no difficulty and 3 indicating inability. Version 96.4 is being used for this study. The independent HAQ assessments for pain and health VAS are also collected.

15.3.14.1. DERIVATION

The standard HAQ-DI will be scored according to the instructions for version 96.4 (National Institute of Environmental Health Sciences, 1996), including the handling of missing values. In summary, the maximum severity reported for each function is averaged across all available functions for the assessment. If an aide or device is used or if help is required from another individual, then the minimum score for that function is 2. The HAQ-DI will be calculated to 3 decimal places.

CFB, PCFB, CFEOT and PCFEOT will be calculated. The following reductions in HAQ-DI score from baseline will be derived: 20%, 50% and 70% (HAQ20, HAQ50 and HAQ70).

15.3.14.2. ANALYSIS

The analyses for HAQ-DI will replicate those performed for CLASI. HAQ20/50/70 will be summarized by treatment.

15.3.15. SF-36

The RAND 36-Item Short Form Health Survey (SF-36; Version 1.0) estimates quality of life indices over 8 components ranging from 0 to 100, over the past four weeks, plus subjects' perception of change in health. Scores represent the percentage of total possible score achieved and higher scores indicates a more favorable health state.

15.3.15.1. DERIVATION

Scoring of the SF-36 will comply with the Rand scoring instructions version 1 (Rand Corporation, 2016), including the handling of missing components. Responses are coded to scores ranging from zero to 100, based on Table 1

Document: SGN35-022 SAP v1 V0.3
Author: [REDACTED]

Version Number: 1.0
Version Date: 31Jan2017

Template No: CS_TP_BS016 – Revision 3
Effective Date: 01Apr2016

Reference: CS_WI_BS005

in the instructions. Groups of scores are then averaged to form the overall score for each component, based on Table 2 of the instructions.

No normalization will be performed on the component scores, in compliance with the version 1 scoring instructions. Summary scores for physical and mental health will be derived from all components of the SF-36 using orthogonal factor scoring coefficients derived from a large sample that allow the components to be correlated, using the 1998 z-scores for the 8 components.

CFB, PCFB, CFEOT and PCFEOT will be calculated for all scores.

15.3.15.2. ANALYSIS

The analyses for SF-36 physical and mental component scores will replicate those performed for CLASI. Summary statistics for the observed scores only will be presented for the 8 SF-36 components.

15.3.16. FACIT-F

Functional Assessment of Chronic Illness Therapy (FACIT) measures subjects' quality of life level (QOL) over the categories of physical, social/family, emotional and functional well-being over 27 questions using on a five-point Likert scale (0 to 4), with higher scores indicating better QOL. A supplementary fatigue score is measured over 13 additional questions using the same scale, for which a score of less than 30 indicates severe fatigue.

15.3.16.1. DERIVATION

The FACIT-F fatigue score, FACIT-F Trial Outcome Index (TOI), Functional Assessment of Cancer Therapy-General (FACT-G), and FACIT-F total score will be calculated from the Likert responses. FACIT-F Scoring Guidelines Version 4 (Cella, 2004) will be used to derive each component score and the following indices:

- FACIT-F fatigue score = weighted sum of available response scores * 13; range 0-52
- FACIT-F Trial Outcome Index (TOI) = weighted sum of available physical, functional, and fatigue scores; range 0-108
- FACT-G total score = weighted sum of available physical, social/family, emotional and functional scores; range 0-108
- FACIT-F total score = weighted sum of available components scores (physical, social/family, emotional, functional, fatigue); range 0-160

CFB, PCFB, CFEOT and PCFEOT will be calculated for all scores.

15.3.16.2. ANALYSIS

The analyses for all FACIT scores will replicate those performed for CLASI. The Likert responses will be listed only.

15.3.17. LUPUSQOL

The LupusQOL measures subjects' quality of life level for the past four weeks over eight domains (physical health, pain, planning, intimate relationship, burden to others, emotional health, body image, fatigue) using 34 questions using on a five-point Likert scale (0 to 4), and yielding scores ranging from 0 to 100, with higher scores indicating better QOL.

15.3.17.1. DERIVATION

Scores for each domain will be calculated as the average of the available Likert responses/4 * 100 (McElhone, 2007). CFB, PCFB, CFEOT and PCFEOT will be calculated for all domains.

15.3.17.2. ANALYSIS

The analyses for all LupusQOL scores will replicate those performed for CLASI.

15.3.18. URINARY CELLULAR CASTS, PYRUIRA AND HEMATURIA

Urinary cellular casts (RBC and WBC only), RBC and WBC in urine are recorded as ordinal categorical results by the clinical labs.

15.3.18.1. DERIVATION

No derivations are required for this analysis.

15.3.18.2. ANALYSIS

Shift tables will be presented, tabulating the number of subjects moving from baseline to the each of the result categories for these laboratory tests. This analysis may be repeated for subjects assessed with active renal disease at any point during the trial, if sufficient sample size is available.

15.3.19. PROTEIN/CREATININE RATIO AND EGFR

Protein/creatinine ratio and eGFR are captured as central laboratory results.

15.3.19.1. DERIVATION

CFB, PCFB, CFEOT and PCFEOT will be calculated for all of these laboratory tests.

15.3.19.2. ANALYSIS

The analyses will replicate those performed for CLASI. This analysis will be repeated for subjects assessed with active renal disease at any point during the trial.

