#### **6.2.3.3 Exploratory**

Exploratory efficacy outcomes include the following:

- proportion of subjects achieving a BICLA response at Day 85;
- proportion of subjects achieving a BILAG clinical response at Day 85
- proportion of subjects achieving a BILAG partial clinical response at Day 85, defined as BILAG C scores or better;

- proportion of subjects achieving a BILAG partial clinical response at Day 85, defined as a maximum of 1 BILAG B score or better;
- proportion of subjects achieving a SLEDAI clinical response at Day 85, defined by a  $\geq 4$  point improvement from baseline;
- proportion of subjects achieving organ-specific BILAG clinical response and partial clinical responses at Day 85 as determined by organ domain-specific scores;
- proportion of subjects achieving 20%, 50%, 70%, and n% (ACR20, ACR50, ACR70, and ACRn, respectively) improvement in SJC and TJC at Days 22, 43, 64, 85, 106, and 127;
- mean and median of observed and percentage change from baseline in SLEDAI, CLASI, TJC, SJC, PtGP, PtGA, PhGA, hsCRP, and ESR at Days 22, 43, 64, 85, 106, and 127;
- mean and median of observed and percentage change from baseline in organ domain-specific SLEDAI scores at Days 22, 43, 64, 85, 106, and 127;
- mean and median of observed and percentage change from baseline in HAQ-DI, SF-36, SF-36 Physical Component Summary (PCS), SF-36 Mental Component Summary (MCS), and FACIT-F at Days 43, 85, and 127;
- mean and median of observed and percentage change from baseline in urinary sediment (cellular casts, pyuria, hematuria), proteinuria (protein/creatinine ratio), and eGFR at Days 22, 43, 64, 85, 106, and 127; and
- mean and median of observed and percentage change from baseline in urinary sediment (cellular casts, pyuria, hematuria), proteinuria (protein/creatinine ratio), and eGFR at Days 22, 43, 64, 85, 106, and 127 in subjects with active renal disease at baseline.

Additional possible exploratory efficacy outcomes include the following:

- median time to treatment failure as defined by:
  - death or need for additional immunosuppressive therapy, or
  - death, end-stage renal disease, doubling of serum creatinine, or SLE or renal flare;
- incidence at Days 22, 43, 64, 85, 106, and 127 of SLE flares using the SELENA and BILAG definitions;
- median time to first mild/moderate and severe SLE flares using SELENA and BILAG definitions;
- incidence at Days 22, 43, 64, 85, 106, and 127 of renal flares;

- median time to first renal flare;

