- mean and median of observed and percentage change from Day 85 in SLEDAI, CLASI, TJC, SJC, PtGP, PtGA, PhGA, hsCRP, and ESR to Days 106 and 127;
- mean and median of observed and percentage change from Day 85 in HAQ-DI, SF-36, SF-36 PCS, SF-36 MCS, and FACIT-F to Day 127;
- mean and median of observed and percentage change from Day 85 in urinary sediment (cellular casts, pyuria, hematuria), proteinuria (protein/creatinine ratio), and eGFR to Days 106 and 127; and
- mean and median of observed and percentage change from Day 85 in urinary sediment (cellular casts, pyuria, hematuria), proteinuria (protein/creatinine ratio), and eGFR to Days 106 and 127 in subjects with active renal disease at baseline.

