### **8.5.4 Subgroup Analysis**

Given the small sample size in this study, no subgroup analyses will be performed.

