3.4. CHANGES TO ANALYSIS FROM PROTOCOL

There are no meaningful deviations from the analyses planned in the study protocol.

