7.5. SUBGROUP ANALYSES

No subgroup analyses will be performed for this study.

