15.3.3.2. ANALYSIS

Observed and change values will be summarized by treatment group. Means with 95% CI will be plotted for Observed and CFB values over time with treatment groups overlaid. Individual values over time will be plotted over time per treatment group.

An analysis of covariance model will be fit for CFB/CFEOT at each scheduled time, with a fixed effect for treatment group and a covariate for the baseline value. Comparisons will be made between each dose level, and all active treated subjects combined versus placebo at the 5% significance level (two-sided). Least-squares treatment means and mean differences will be estimated with 95% CI and two-sided p-values for the test of no treatment difference.

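### The SAP selects the renal subset on disease at any time in the trial, where the protocol says at baseline, without declaring it; and time to first oral steroid use has no rule for subjects who enter on steroids

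*SAP*

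**What the plan says.** **Renal subset.** Protocol 6.2.3.3 lists changes in urinary sediment, proteinuria and eGFR for all subjects and again "in subjects with active renal disease at baseline". It repeats the restriction for change from Day 85: "to Days 106 and 127 in subjects with active renal disease at baseline". SAP 15.3.19.2 (protein/creatinine ratio and eGFR) has "This analysis will be repeated for subjects assessed with active renal disease at any point during the trial". SAP 15.3.18.2 (casts, pyuria, hematuria) has "This analysis may be repeated for subjects assessed with active renal disease at any point during the trial", subject to sufficient sample size. SAP 3.4 states: "There are no meaningful deviations from the analyses planned in the study protocol". On subgroups, SAP 7.5 has "No subgroup analyses will be performed for this study", and protocol 8.5.4 has "Given the small sample size in this study, no subgroup analyses will be performed".

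Protocol 6.2.2 defines active renal disease as a urinary protein:creatinine ratio of at least 0.5 with active sediment, or isolated severe proteinuria. SAP 15.3.19.2 copies the CLASI analysis in SAP 15.3.3.2: "Observed and change values will be summarized by treatment group", followed by an ANCOVA with baseline as covariate.

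**Oral corticosteroids.** Inclusion criterion 9 and protocol 5.7.2 admit subjects on stable corticosteroids and expect them to continue. SAP 13 counts a drug begun before consent and still ongoing as concomitant. SAP 15.3.12 reads oral steroid use from the concomitant medication panel, scores it present or absent for each postdose interval, and takes time to first use by SAP 15.1, from randomisation. It then applies Kaplan-Meier methods and the SRI response analyses.

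**Active renal disease.** SAP 15.3.11 takes time to first diagnosis in the same way.

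**The concern.** A subset defined at baseline is fixed before treatment can act. One defined by disease at any visit is not: if the drug lowers proteinuria, fewer active subjects cross the threshold after baseline, and those who qualify tend to have started higher. The arms being compared then differ at baseline, and the observed, change and adjusted summaries can disagree. The ratio both helps select the subjects and is the outcome analysed in them. The SAP does not record the switch as a change.

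For steroids, a subject already taking them at randomisation has no first use to wait for. By recorded start date the time is zero or negative. By the postdose intervals, which begin the day after the previous visit, the event falls on Day 2. No rule excludes these subjects, limits the event to new use or assigns a date. The curve and the visit-level ratios then mix prevalent use with new use, which dilutes any effect. Time to first active renal disease has the same gap for subjects who have the condition on Day 1.

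**Working it through.** The documents give no figure for these analyses to reproduce; sample size was set by clinical judgment. The two discrepancies are established by the text above. The sizes below rest on assumed inputs.

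**1. Renal subset.** From the documents: ratio cut 0.5, severe proteinuria taken as ratio 3.5, six post-baseline efficacy visits with Day 85 the fourth, 8 subjects per dose arm and 8 pooled placebo. Assumed: log-normal ratio with median 0.3, between-subject log SD 0.9, within-subject log SD 0.4, and a drug effect of 0.70 from the first post-baseline visit. Active sediment is assumed in 50% or 25% of assessments (between-visit correlation 0.5), or ignored. Simulated with 200,000 subjects per arm:

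| | Sediment 50% | Sediment 25% | Ratio only |
|---|---|---|---|
| Qualify at baseline, either arm | 15% | 8% | 30% |
| Qualify at any point, placebo v active | 38% v 29% | 26% v 18% | 51% v 40% |
| Members without disease at baseline, placebo v active | 60% v 46% | 68% v 57% | 41% v 25% |
| Members' baseline ratio, active/placebo | 1.22 | 1.21 | 1.22 |
| Day 85, observed values | 0.82 | 0.82 | 0.82 |
| Day 85, unadjusted change | 0.67 | 0.68 | 0.67 |
| Day 85, ANCOVA | 0.72 | 0.72 | 0.72 |
| Day 85, ANCOVA, baseline subset | 0.70 | 0.70 | 0.70 |

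With no drug effect, the any-point rule returns 0.99 to 1.01. Letting the within-subject SD run from 0.2 to 0.6 widens the ranges: observed values about 0.80 to 0.83, change 0.67 to 0.69, ANCOVA 0.69 to 0.74. Members without baseline disease then run from 6% to 70%, depending on arm and assumptions.

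Size of the ANCOVA shift (sediment 50%):
- Expected members: 8 × 0.384 = 3.1 placebo and 8 × 0.289 = 2.3 active.
- With residual log SD 0.53, SE = 0.53 × √(1/3.1 + 1/2.3) = 0.46.
- Shift = ln(0.722/0.70) = 0.03, about 7% of one SE.

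Size of the baseline subset, with q the share qualifying: 8q = 1.2, 0.6 or 2.4 per arm. The chance of an empty arm is (1 − q)^8 = 27%, 51% or 6%.

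**2. Steroids.** The documents do not give the share p of subjects on steroids on Day 1. Assume p = 20%, 50% or 80%, with new use in 20% of active and 40% of placebo non-users (risk ratio 0.50, difference 20 points). Diluted ratio = [p + (1 − p) × 0.2] / [p + (1 − p) × 0.4]:

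- p = 0.2: 0.36/0.52 = 0.69, difference 16 points
- p = 0.5: 0.60/0.70 = 0.86, difference 10 points
- p = 0.8: 0.84/0.88 = 0.95, difference 4 points

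The Kaplan-Meier curve of an arm of 8 starts at or below 0.50 when at least 4 are Day 1 users. By the binomial(8, p) tail this has probability 6%, 64% or 99%. A chance imbalance in Day 1 users alone reaches Fisher p ≤ 0.05 in 0.4%, 2.1% or 0.4% of comparisons, so the harm is dilution and not a false signal.

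**The case against.** Every affected output is exploratory, in a study the SAP calls hypothesis-generating, without multiplicity control. The renal change from Day 85 is only an additional possible outcome in the protocol, the sediment repeat is optional, and time to steroid use and time to active renal disease are SAP additions. The planned test is the baseline-adjusted ANCOVA, which moves from 0.70 to 0.72, and hardly at all with a within-subject SD of 0.2. The simulation counts any single-visit threshold crossing, whereas SAP 15.3.11 relies on occurrences recorded on the eCRF. A baseline subset may be nearly empty. The no-subgroup tension begins in the protocol, where 6.2.3.3 lists the subset and 8.5.4 bars subgroups; it can be read as no further subgroups. Steroid increases are already counted in treatment failure (SAP 15.3.13) and in SELENA flares (SAP 15.3.8).

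Most of this stands, and it sets the priority. It does not remove the undeclared change of rule or the missing rule for prevalent users. A small subset is a reason for a sample-size condition, not for selecting on outcome.

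Three stronger readings are tempting and are not supported:
- That the any-point rule would manufacture a renal effect. Under the null both arms are selected alike.
- That the steroid curve would mostly show who entered on steroids. At 20% Day 1 use it would not, and the documents do not state the share.
- That present/absent scoring is wrong because it hides dose reductions. No protocol endpoint concerns steroid sparing, so that is a preference.

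**Conclusion.** The concern holds as two textual defects with limited consequences. The SAP replaces a baseline-defined renal subset with one that depends on post-randomisation status and does not declare it. Under the stated assumptions the descriptive summaries would disagree, but the ANCOVA bias is small (0.69 to 0.74 against 0.70), particularly beside the imprecision of two or three members per arm. A reader might infer that the renal treatment comparison is invalid; the planned adjusted analysis does not bear that out.

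The steroid endpoint, as written, turns prevalent users into events at or before the first postdose interval. The resulting dilution is modest or near complete depending on a share of Day 1 users that the documents do not give. The same gap in time to first active renal disease is clear from the text, but no size is put on it here. The primary safety objective and SRI are unaffected. Priority: minor correction before unblinding.

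**What to change.** (a) In SAP 15.3.18.2 and 15.3.19.2, restore active renal disease at baseline as the selection rule, and carry the sample-size condition from 15.3.18.2 to 15.3.19.2. Keep any any-point set only as a labelled sensitivity analysis declared in SAP 3.4. Name the baseline renal subset as the exception in SAP 7.5 and protocol 8.5.4.

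(b) In SAP 15.3.12, define both the time-to-event and the visit-level event as the first oral corticosteroid start among subjects not taking them on Day 1, and report the number of Day 1 users per arm.

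(c) In SAP 15.3.11, apply the same at-risk rule: count first active renal disease only in subjects without it on Day 1.

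The cost is SAP wording, a few derivations and one protocol clarification, all before unblinding. Fewer subjects are at risk: at 20%, 50% or 80% Day 1 use, 8 × (1 − p) = 6.4, 4.0 or 1.6 steroid non-users per arm of 8. The baseline renal subset will be very small and may be empty in some arms, in which case listing the subjects is all that can be done.
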